Official title: Exacerbation in severe asthma patients: mechanisms and biomarkers NCT02660853

Document date: 08/05/2013

Background

Exacerbations are important events in asthma and represent an important burden for the patient. The risk of experiencing an exacerbation is greatest in the patient with severe asthma, who already experiences daily symptoms, impaired lung function and adverse effects from corticosteroid therapy despite using maximal amounts of anti-asthma therapies particularly corticosteroids(1;2). In the SARP severe asthma cohort, 40% of patients required one or more emergency department visits, compared to 20% and 15% in moderate and mild asthma groups respectively(3); for those using >3 oral corticosteroid bursts in the past year, this was 54% in severe, 13% in moderate and 5% in mild. In the UK BTS cohort, up to 89% of severe asthma patients required one or more courses of high dose prednisolone in the previous year(4). Exacerbations are occurring even while on maximal doses of therapy.

According to the ERS/ATS Task Force on Asthma Control and Exacerbations(5), the definition of an asthma exacerbation is based on deterioration of symptoms that needs urgent action with the need to use of systemic corticosteroids defining severe exacerbations, and those without the needing for corticosteroids or increasing corticosteroids defining moderate exacerbations. However, these definitions while useful in clinical trials are not adequate for health care professionals and for patients, where a prospective definition is needed. There has been relatively few studies examining the circumstances of an exacerbation. In patients with mild-to-moderate asthma, exacerbations were characterized by a gradual fall in peak expiratory flows (PEF) over several days, followed by more rapid changes over 2 to 3 days with a parallel increase in symptoms and rescue beta-agonist use(6), which was unaffected by the use of inhaled corticosteroids or of a long-acting beta-agonist. Very little is known about the course and severity of these exacerbations in severe asthma. We hypothesise that the causes of an exacerbation in severe asthma may be different than those in non-severe asthma.

Causes of exacerbations

Viral respiratory tract infections have been recognised as triggers for exacerbations of asthma with rhinoviruses being the most common virus(7). Bacteria have also been associated with exacerbations including atypical *Mycoplasma pneumonia* and *Chlamydiae pneumonia*, in 27% of

1

Title: Exacerbation in severe asthma patients: mechanisms and biomarkers

exacerbations(8). In stable patients with severe asthma from RBH, ~50% of sputum cultures were positive for bacteria, and this was more likely in those with an exacerbation in the previous year (9). Microbiome studies of the lower airways of asthma have indicated a more diverse microbial population compared to non-asthma subjects(10;11). In collaboration with Professors [name] and [name] (NHLI), we performed microbiome studies on sputum samples and bronchial brushings in patients with severe asthma and found that Streptococcus operational taxonomic units were more abundant in severe asthma sputum samples than in non-severe asthmatics and healthy subjects(12). The potential role of bacterial infections during exacerbations is supported by the observation that a macrolide antibiotic provided a small but significant benefit in accelerating the recovery period (13). It is possible that bacterial infections may play a greater part in the exacerbation observed in patients with severe asthma. However viral infections may also be important. We have recently shown that blood CD8⁺ T cells from severe asthma were markedly activated in terms of expression of T cell activation markers and of MAP kinases, JAK/STAT and the transcription factor, NF-κB (14), with one potential explanation being the activation from viruses. Viral infections may also increase the chance of a bacterial reactivation, as has been shown in virus-induced COPD exacerbations (15).

Exacerbations in severe asthma may also be related to the deranged innate immune responses to infective agents. A reduced interferon response to rhinovirus infections of the asthmatic airways has been described (16), allowing for increased viral replication leading to an increased inflammatory response. In severe asthmatic, we have found a reduction in the ability of the alveolar macrophage and of the monocyte-derived macrophage (MDM) in phagocytosing beads coated with Staph aureus and Haem influenzae (unpublished; Fig 1). Rhinoviruses could also impair phagocytosis of bacteria by macrophages(17). A defective response in the phagocytosis of apoptotic cells ('efferocytosis') of macrophages from severe asthma and from neutrophilic asthma has also been described(18;19). The impaired phagocytosis has been associated with an intracellular imbalance of glutathione sulphide homeostasis, together with a reduction in histone deacetylase activity (20). In adult asthmatics, an exacerbation is characterised by a neutrophilic inflammation in sputum (21), and rhinovirus-induced asthma exacerbations is also accompanied by a neutrophilic response (22), although rhinovirus has also been associated with an activation of Th-2 mechanisms. The high Th2 phenotype characterised by eosinophilic asthma is highly prone to exacerbations (23). The potential for an interaction between viral infections, allergen exposure and atopic sensitisation as conferring the greatest risk has been proposed(24).

Viral and bacterial infections can both contribute to oxidative stress and have also been associated with the generation of reactive oxygen species through the induction of inflammation, with down-regulation of antioxidant defences. Elevated levels of 8-isoprostanes have been measured in sputum infected with bacteria(25). Oxidative stress occurs after allergen challenge, with a rapid loss of superoxide dismutase activity(26). Lower airway levels of GSH with increased GSSG in bronchoalveolar lavage fluid has been reported in asthmatic children with elevated levels of malondialdehyde, 8-isoprostanes and $H_2O_2(20)$. Increased oxidant stress has been seen as a constant feature of severe asthma(27). During an exacerbation, there may be a further augmentation of oxidative stress that may in turn contribute to airway smooth muscle contraction, inflammation and corticosteroid insensitivity(28). We have demonstrated the presence of CS insensitivity in macrophages and airway smooth muscle cells from patients with severe asthma(29;30). This may contribute to the lack of effect of corticosteroids in controlling the deterioration in asthma. Finally, activation of MAP kinases, JAK/STAT and the transcription factor, NF- κ B, in blood CD8⁺ T-cells of patients with severe asthma may contribute to greater risk of exacerbations(14).

Heterogeneity and Biomarkers of exacerbations

Because of the different potential causes associated with exacerbations in patients with severe asthma, it is likely that there are different phenotypes. This is important to determine because more specifically-targeted treatments for exacerbations may lead to better resolution without the need to use or increase corticosteroid use. There are also no biomarkers identified for the detection or for quantifying the severity of an exacerbation, and that would also be valuable in patients with severe asthma who are already taking medication that could influence the levels of biomarkers. One potential improvement may result from an earlier detection of the exacerbation and therefore a biomarker for an earlier detection of exacerbation in severe asthma would be useful, particularly for initiation of treatments.

Hypothesis and objectives

We hypothesise that (i) exacerbations in severe asthma are causally heterogeneous and (ii) represent a corticosteroid-insensitive event caused by an excess of oxidants and inflammation resulting from respiratory viral and bacterial agents.

The *objectives* of this project are to:

- determine the symptoms and lung function characteristics and course of asthma exacerbations in patients with severe asthma
- (ii) evaluate the role of infective agents (respiratory viruses and bacteria)

3

- (iii) define the biomarkers in exhaled breath, sputum and in blood
- (iv) study the presence of oxidative stress, phagocytic capacity of macrophages and corticosteroid insensitivity.

Major outcomes of this study will be (i) to assess the feasibility of diagnosing exacerbations earlier (ii) to determine the heterogeneity of the presentation and course of exacerbations (iii) to identify exacerbation phenotypes in terms of causes and (iv) to look for potential targets for treatment.

Study design

We have a database of 300 current patients with severe asthma defined according to ATS criteria(1) with exacerbation rate of 1.5 ± 2.8 (SD)/year. To achieve 1.7 exacerbations after 16 weeks will require 36 patients at 90% power and 5% significance. Adjusting for a possible dropout of 30% would require 56 patients. Therefore, 60 patients will be recruited. To be on the safe side, we will enrol patients with a history of \geq 3 exacerbations/year for a prospective observational study.

At entry Visit 1, we will enrol and characterise these patients. They will be observed over 12 months during which the number of exacerbations will be recorded on the basis of objective measures with evaluation of ACQ and daily morning and evening PEF. At the earliest onset of each exacerbation, the patient will be requested to contact by phone the Asthma BRU Unit. For one of these events, patients will be asked to attend the laboratory for a series of tests at Visit 2 similar to Visit 1. Visit 3 will be planned within 14 days after Visit 2, when the patient has recovered.

In 30 of the 60 patients, we will request for an additional attendance of a subsequent exacerbation (Visit 4) with follow-up (Visit 5). For other exacerbations not studied, the patient will be asked to keep a detailed diary record of symptoms with severity scoring and spirometric and PEF measurements (Exacerbation Diary) over a period of 2 weeks after the onset of exacerbation.

Patients will have their exacerbations treated in the usual way. The only exception will be the use of antibiotics which will be withheld and initiated (if indicated) after the patients has been through Visit 2. Those who have to be hospitalised will not be studied, and only those who can attend the Clinical Research Unit will be studied. The more severe exacerbations will therefore be missed but will be recorded in the patient's diary.

Tests to be performed Visits 1, 2 and 3:

1. Diary of symptom scores, use of beta-agonist reliever and other treatments for 2 weeks

- 2. PEFR and spirometry twice daily for 2 weeks
- 3. Markers of systemic inflammation in blood: CRP, IL-8, IL-6, together with Meso-Scale-Discovery (MSD) platform for other cytokines.
- 4. Markers of oxidative stress in blood, exhaled breath condensate (EBC) and urine: malondialdehyde (MDA) and 8-isoprostanes (31).
- Nitric oxide (NO) levels in exhaled breath measured twice daily for 2 weeks using a portable hand-held NO meter (NO_{breath}). EBC for pH & free iron (32)
- 6. Induced or spontaneous sputum for inflammatory cells and assays of cytokines in supernatants using Meso-Scale-Discovery (MSD) platform, bacteriological culture and for microbiome analysis. H₂S which is elevated in asthma in relation to sputum neutrophil counts (33)will also be measured. If spontaneous sputum is not available, sputum will be induced using ultrasonic nebulization of isotonic saline (34), which is safe in patients during an exacerbation (35).
- 7. Sputum for bacteriological culture and colony forming units.
- 8. PCR for respiratory viruses from nasopharyngeal swabs and sputum RNA and reverse transcription performed for respiratory viruses including rhinovirus, influenza virus types A and B, parainfluenza viruses 1 to 3, coronaviruses and respiratory syncytial virus types A and B, and Chlamydia pneumonia, and Mycoplasma pneumonia using real-time 'TaqMan' assays in collaboration with [name], NHLI.
- Sputum microbiome: 16S rRNA PCR and pyrosequencing will be performed on sputum with amplification of the V3-V5 regions (36) in collaboration with Professors [name] and [name], NHLI.
- 10. Studies on blood cells:
 - MDM's phagocytosis of fluorescently-labelled Pseudomonas aeruginosa and Staphylococcus aureus ([name], NHLI) on macrophage-derived monocytes as described previously (37)
 - (ii) Transcriptomic analysis of blood CD4⁺ and CD8⁺ T-cells and monocytes, as previously described (14)
 - Studies of corticosteroid insensitivity in peripheral blood mononuclear cells and in whole blood ([name], NHLI) (38)

Definition of exacerbation and monitoring

Because these patients with severe asthma are usually well-experienced 'exacerbators', they will be asked to 'diagnose' their own exacerbations. Each has an individualised way of recognising an

exacerbation. We will discuss with each patient t their way of recognising a deterioration and try and work out whether earlier signal warning is possible. One of our aims is to find out what the objective measures of deterioration are. We will also ask patients to record their symptoms and lung function as soon as they feel the onset of an exacerbation, since exacerbations are recognised by the patient as events that are 'clinically identified by being outside the patient's usual range of day-to-day asthma variation'(5). They will also contact the Study Coordinator (Nurse or Clinical Research Fellow) to determine if they can attend for Visit 2. The patient will receive or administer treatments for the exacerbation as usual without interference from the Research team. Except for the exacerbation that will be studied (Visit 2 or Visit 4), the patient will be requested to refrain from starting any antibiotic therapies, which will be started (if this has been prescribed) as soon as Visit 2 studies have been completed.

Data analysis

- The daily variation of symptoms and lung function during the exacerbation visits (2 and 4) will be analysed, and related to the changes observed in the various parameters collected at exacerbation. Comparison of these biomarkers to those at Visit 1 and at the recovery visit will allow for ascertainment of biomarkers that may be associated with exacerbations. Bacterial- or virusassociated, or eosinophil- or neutrophil-associated exacerbation will be defined.
- 2. Unbiased mathematical methods such as factor and cluster analyses will be used to identify factors at exacerbations and classify groups of similar characteristics looking at all the data collected including the transcriptomic and cytokine profile data. The analysis will be performed by the Bioinformatics group led by [name] of Discovery Science at Imperial College.
- 3. The stability of the exacerbation profile will be examined within the 30 patients who have had a repeat exacerbation visit. We could also look at this small group as a validation data set.

Timelines and milestones

Oct 2013-Dec 2013: Setting up of study, identification of patients, setting up methods. Jan 2014-Dec 2014: Recruitment of 30 patients, and follow up to Dec 2014 Jan 2015-Dec 2015: Recruitment of 30 patients, and follow up to Dec 2015 Jan 2016-Sept 2016: Completion of assays, analysis of data, biomarker validation

Future plans of research

 Information obtained from this study will allow us to plan better any future therapeutic studies on asthma exacerbations and will also provide us with an idea of targets for treatments for particular types of exacerbations. Therefore, we plan to use the new information gathered to plan for future studies (eg the number of subjects needed for a therapeutic study).

One target of therapy that we are seeking confirmation for is that of oxidant stress. Currently there are no good antioxidants, but N-acetylcysteine or other similar medications is available and could be tested as treatment for exacerbations. We will also test drugs not only for treating exacerbations, but also for reducing exacerbation rate. This may include approaches to reduce corticosteroid insensitivity since the recurrence of exacerbations in patients taking high dose corticosteroids is a reflection of corticosteroid insensitivity. p38 MAPK inhibitors may be such a drug (39).

- 2. There will be a need for validation of some of the identified biomarkers for each exacerbation phenotype, and this will be done in multicentre studies in collaboration with other Centres within the BTS Severe Asthma Group.
- 3. This research will also provide information about the best tools to monitor exacerbations in severe asthma patients. This will be examined in newly-recruited patients to our cohort.

Reference List

- (1) Proceedings of the ATS workshop on refractory asthma: current understanding, recommendations, and unanswered questions. Am J Respir Crit Care Med 2000 December;162(6):2341-51.

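### The figures 36 patients, 30% dropout and 56 patients do not agree, and the plan's only power statement, on a 16-week exacerbation count, covers none of the planned analyses

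*Combined protocol and SAP*

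**What the plan says.** The whole sample-size argument is in one paragraph of the Study design section. It starts from a database of 300 patients with severe asthma "with exacerbation rate of 1.5 ± 2.8 (SD)/year". It continues: "To achieve 1.7 exacerbations after 16 weeks will require 36 patients at 90% power and 5% significance". The dropout step follows: "Adjusting for a possible dropout of 30% would require 56 patients". The conclusion is: "Therefore, 60 patients will be recruited". As an extra margin, entry is limited to patients with a history of at least three exacerbations a year.

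The same section sets follow-up at a year: "They will be observed over 12 months during which the number of exacerbations will be recorded". Patients admitted to hospital do not contribute laboratory data: "Those who have to be hospitalised will not be studied, and only those who can attend the Clinical Research Unit will be studied".

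The Data analysis section lists three items:

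- Daily symptoms and lung function are related to the other measurements, biomarkers are compared across visits ("Comparison of these biomarkers to those at Visit 1 and at the recovery visit will allow for ascertainment of biomarkers"), and exacerbations are grouped as bacterial, viral, eosinophilic or neutrophilic.
- Exploratory multivariate work: "Unbiased mathematical methods such as factor and cluster analyses will be used to identify factors at exacerbations".
- Stability of the exacerbation profile is examined in the 30 patients with a repeat exacerbation visit.

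No other power or precision statement appears.

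**The concern.** There are two separate problems.

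First, the step from 36 to 56 does not follow from a 30% dropout under either common way of inflating a sample size. A reader cannot tell whether the base, the dropout rate or the result is misprinted.

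Second, the power statement concerns 1.7 exacerbations in 16 weeks and stands beside a rate and SD that are both annual. It names no null value, test, sidedness or 16-week SD. More importantly, no listed analysis tests the number or rate of exacerbations, and none uses a 16-week time point. The plan tells its readers that the study has 90% power, but not for any question it intends to analyse. Because this is the stated basis for recruiting 60, a reader could carry that 90% over to the biomarker or infection results, where it does not apply.

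**Working it through.** **Inputs, all from Study design.** Base 36; power 90%; significance 5% (sidedness not given); target 1.7 in 16 weeks; rate 1.5 per year, SD 2.8; dropout 30%; inflated number 56; recruited 60.

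**1. Dropout step (stated result: 56)**

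- Dividing by the retained fraction: 36/(1 - 0.30) = 51.4, so 52.
- Multiplying up: 36 x 1.30 = 46.8, so 47.
- Base needed for 56 at 30%: 56 x 0.7 = 39.2. Checking whole numbers, 38/0.7 = 54.3 (55), 39/0.7 = 55.7 (56) and 40/0.7 = 57.1 (58), so only 39 works.
- Dropout needed for 56 from 36: 1 - 36/56 = 35.7% exactly. Allowing for rounding up, 36/(1 - 0.346) = 55.05 also gives 56, so about 34.6% to 35.7% would do.
- Patients left after 30% dropout from 60: 60 x 0.7 = 42, above both 36 and 39.

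**2. Can 36 be reproduced?** The time scales differ: 1.5 per year is 1.5 x 16/52 = 0.46 per 16 weeks, and 1.7 per 16 weeks is 1.7 x 52/16 = 5.5 per year. The test is not named, so a one-sample test is assumed, two-sided 5%, 90% power:

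n = (1.960 + 1.282)^2 x SD^2 / difference^2

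| Reading (assumed) | Normal formula | t-test |
|---|---|---|
| Difference 1.7, SD 2.8 | 28.5, so 29 | 31 |
| Difference 1.5, SD 2.8 | 36.6, so 37 | 39 |
| Difference 1.7 - 0.46 = 1.24, SD 2.8 | 53.7, so 54 | 56 |
| Difference 1.24, SD 2.8 x sqrt(16/52) = 1.55 | 16.5, so 17 | 19 |

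The second row comes closest to the plan. It gives 37 or 39, and 39/0.7 gives the stated 56. At exactly 36 patients its t-test power is 87.8%; at 39 it is 90.3%. It uses neither the 1.7 nor the 16 weeks, so it does not explain the sentence as printed. (The 56 in the third row is a number before dropout, so it does not explain the plan's inflated figure.)

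**3. What the power statement covers**

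| Planned analysis | Tests an exacerbation count or rate? | Uses 16 weeks? |
|---|---|---|
| Daily symptoms and lung function related to other measurements | No | No |
| Biomarkers at exacerbation against Visit 1 and recovery | No | No |
| Infection and inflammatory-cell grouping | No | No |
| Factor and cluster analyses | No | No |
| Profile stability in 30 patients | No | No |

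**4. Illustration of what 60 patients could offer.** The plan specifies no paired test and no infection proportion; both are assumed here.

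- Paired t-test, one marker, two-sided 5%, 90% power, before multiplicity adjustment: 0.51 SD detectable with 42 pairs and 0.56 SD with 36.
- 95% CI half-width for an assumed 50% infection proportion with 42 patients: 1.96 x sqrt(0.25/42) = 0.151, about 15 percentage points.

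**The case against.** The strongest reply is that the sentence is a yield calculation. It speaks of achieving a number of exacerbations, and the entry criterion is then tightened as a safety margin. Every analysis needs observed exacerbations, so planning for enough of them is sensible. This reading is fair and probably close to the intention. It softens the criticism but does not remove it: on this reading, 90% power and 5% significance have no stated hypothesis, and the figure still does not carry over to the analyses made on those exacerbations.

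A second reply is that the arithmetic slip does no harm. That stands. Fifty-six exceeds 52, and 60 exceeds both. A reader might infer from the mismatch that the study recruits too few patients; the figures show the opposite for the dropout step.

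A third reply is that the study is observational and exploratory, with validation of biomarkers left to later multicentre work, so no formal power is needed. That also stands, and it is why a precision statement is offered only as an option. It is not a reason to keep a 90% power claim that attaches to nothing in the analysis section.

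Two further inferences are tempting and should not be drawn. One is that 36 is disproved because some readings give very different numbers. The extreme case, 1.7 against 1.5 with SD 2.8, needs about 2,060 patients, but it subtracts an annual rate from a 16-week count, which is unlikely to have been meant. The other is that 36 is certainly a misprint for 39. That fits the 56 but leaves the 1.7 and the 16 weeks unexplained.

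**Conclusion.** The point holds in two parts of unequal weight.

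The smaller part needs no outside assumption: 36, 30% and 56 cannot all be right. If 36 and 30% stand, the inflated number is 52, four fewer than stated. If 56 and 30% stand, the base is 39. The documents do not show which figure slipped. The error is on the safe side, and the 60 to be recruited need not change.

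The larger part is that the only stated power concerns a quantity that no planned analysis tests, so it gives no support to the biomarker, infection, factor and cluster, or stability results. This rests on a reading of the Study design and Data analysis sections, not on a calculation. The missing null value, test, sidedness and 16-week SD mean that 36 is unverified, not that it is wrong; on their own these would be missing detail.

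None of this shows that 60 is too few for the exploratory aims. The precision figures rest on an assumed paired test, 42 complete pairs and a 50% infection proportion, and they do not cover multiplicity or clustering. Complete pairs could be fewer than 42 if patients have no attended exacerbation, are hospitalised or give no sputum.

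This should be fixed, by wording alone.

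**What to change.** Keep 60 patients.

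- **(a) Reconcile the figures.** State the base, dropout and inflated number so that they agree: 52 if 36 and 30% stand; a base of 39 if 56 and 30% stand.
- **(b) Stop presenting 90% power as support for the planned analyses.** Either remove it, or label it as an exacerbation-yield calculation with its null value, test, sidedness and 16-week SD. If it is kept, say that it does not cover the biomarker, infection or cluster analyses.
- **(c) Optionally, add a precision statement marked as an illustration.** Use the detectable difference for a single marker with 42 and 36 pairs and the confidence interval for an assumed infection proportion, as worked above, and say that multiplicity is not allowed for.

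The cost is protocol wording: no extra patients, visits or assays, and no primary marker has to be chosen, because the illustration is per marker in SD units. The downside is that a stated 90% power gives way to a less favourable, openly exploratory statement.

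### The antibiotic rule in Definition of exacerbation and monitoring is reversed as punctuated, and both release clauses leave out Visit 4

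*Combined protocol and SAP*

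**What the plan says.** Two places in the combined protocol and SAP set the antibiotic rule.

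- **Study design**, in the paragraph before the test list, says exacerbations are managed in the usual way and then adds: "The only exception will be the use of antibiotics which will be withheld and initiated (if indicated) after the patients has been through Visit 2".
- **Definition of exacerbation and monitoring** first states the default: "The patient will receive or administer treatments for the exacerbation as usual without interference from the Research team". The next sentence reads: "Except for the exacerbation that will be studied (Visit 2 or Visit 4), the patient will be requested to refrain from starting any antibiotic therapies", and ends with the release point: "which will be started (if this has been prescribed) as soon as Visit 2 studies have been completed".

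Three other statements bear on the reading.

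- Visit 4 belongs to a later event than Visit 2: "In 30 of the 60 patients, we will request for an additional attendance of a subsequent exacerbation" (Study design).
- Exacerbations without a study visit are followed at home: "For other exacerbations not studied, the patient will be asked to keep a detailed diary record of symptoms with severity scoring" (Study design).
- The analysis uses both exacerbation visits: "The daily variation of symptoms and lung function during the exacerbation visits (2 and 4) will be analysed" (Data analysis, item 1). Item 3 examines the stability of the profile in the 30 patients with a repeat exacerbation visit and suggests they might also serve as a validation set.

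The test list includes sputum culture, colony counts and 16S sequencing. Its heading covers Visits 1, 2 and 3 only.

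**The concern.** There are two separate faults of wording.

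The first is the scope of the hold. The opening words of the operative sentence remove the studied exacerbations from the request to hold off antibiotics, so the request lands on the unstudied ones. That is the opposite of Study design.

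The second is the release point. Both sections end the hold when Visit 2 is complete. Neither says what ends it for the exacerbation seen at Visit 4.

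Wording matters here because patients diagnose their own exacerbations and may treat themselves before they attend. Usual care is the default, so a hold works only if it is stated as a clear exception that the patient understands beforehand. If antibiotics came first, bacterial culture, colony counts and 16S results would be altered before sampling. Those results serve objective (ii), on the role of viruses and bacteria, and the definition of bacterial-associated exacerbations. They also enter the comparison of Visit 2 with Visit 4, where a drug effect at one visit could pass for a change in exacerbation profile. Meanwhile the literal rule would delay treatment in exacerbations from which no sample is taken.

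**Working it through.** The plan gives no figure to reproduce. The check is textual, followed by an illustration of scale.

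**Step 1: scope of the hold.**

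| Place | Studied exacerbation | Unstudied exacerbation |
|---|---|---|
| Study design | Held until Visit 2 | Hold not addressed separately; usual treatment is the default |
| Definition section, default sentence | Usual treatment | Usual treatment |
| Definition section, next sentence as punctuated | Exempt from the hold | Held |

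The last row contradicts the other two. It also contradicts its own ending: an unstudied exacerbation has a diary and no study visit, so nothing would ever release the hold.

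**Step 2: release point.** Visit 4 occurs at an exacerbation after the one seen at Visit 2. The only stated release condition, completion of Visit 2, has therefore been met before the Visit 4 exacerbation begins. Read literally, neither section makes antibiotics wait for Visit 4 sampling. Repairing Step 1 does not repair this.

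**Step 3: what is sampled at Visit 4.** No test list names Visit 4. Sampling there is implied by Data analysis items 1 and 3, which need exacerbation data from it. The exposure below depends on that inference.

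**Step 4: scale.** Planned studied exacerbations are 60 at Visit 2 plus 30 at Visit 4, or 90 before dropout. The release gap concerns up to 30 of them (30/90, one third).

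Inputs for the illustration:

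- n = 30 pairs (Study design).
- Culture-positive share c = 0.5 (Causes of exacerbations; reported for stable patients, not during exacerbations).
- p, the share of Visit 4 exacerbations already on antibiotics at sampling: assumed 0.10, 0.25 or 0.50.
- q, the share of positive cultures turned negative: assumed 0.5 to 1.0.
- Visit 2 sampled before antibiotics, and prescribing independent of culture status: both assumed.

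Affected Visit 4 samples = n × p = 3, 7.5 or 15.

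A pair falsely looks changed only if both visits are truly positive and the second is turned negative.

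- *Perfect concordance between visits:* the both-positive share is 0.5, so the count is 30 × 0.5 × p × q.
- *Independence between visits:* the both-positive share is 0.5 × 0.5 = 0.25, so the count is 30 × 0.25 × p × q.

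| p | q | Perfect concordance | Independence |
|---|---|---|---|
| 0.10 | 0.5 | 0.75 (2.5%) | 0.375 (1.25%) |
| 0.25 | 0.5 | 1.875 (6.25%) | 0.9375 (3.125%) |
| 0.25 | 1.0 | 3.75 (12.5%) | 1.875 (6.25%) |
| 0.50 | 1.0 | 7.5 (25%) | 3.75 (12.5%) |

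Under independence there is an equal and opposite error. Pairs truly negative at Visit 2 and positive at Visit 4 also have share 0.5 × 0.5 = 0.25, and conversion would make them look stable. If the intended rule is followed, p = 0 and every entry is 0.

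**The case against.** The best reply is that this is a slip of punctuation. Join the opening words of the operative sentence to the sentence before it and the sense is: no interference with treatment, except that in the studied exacerbation (Visit 2 or Visit 4) antibiotics wait. That agrees with Study design and brings Visit 4 inside the hold. The literal reading also defeats itself, since unstudied events have no visit to release them, so staff are unlikely to apply it. This stands as a guide to intent. It does not supply a release point for Visit 4.

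A second reply is that Visit 2 may be shorthand for whichever exacerbation visit is being studied. The same paragraph asks patients to call about attending Visit 2 without mentioning Visit 4. The test list likewise omits Visit 4, so one who reads strictly should find no listed Visit 4 culture to contaminate, and one who carries the Visit 2 tests over should carry the release point over too. This is fair and limits the claim. The release clauses omit Visit 4, but that does not show that the authors meant no hold there.

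Third, patients are asked to telephone at the earliest onset, which favours sampling before antibiotics even without a clear rule. That also stands, though its effect cannot be measured from the documents.

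Two stronger readings are tempting. A reader might infer that Visit 4 samples will in fact be post-antibiotic, or that a quarter of the repeat pairs will be misread. The documents support neither: p and q have no basis in them, and 25% is the top of a range that also needs perfect concordance, which is what the stability analysis is meant to learn. A reader might also infer that the study intends to deny antibiotics in unstudied exacerbations. The default of usual care, stated in both sections, shows otherwise.

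**Conclusion.** The point holds as a fault in a stated operating rule. The sentence in Definition of exacerbation and monitoring reverses the scope of the hold, and the release clauses in both sections omit Visit 4. Visit 2 still has a clear hold in Study design, which the later sentence contradicts.

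The harm is conditional on the text being followed as written. Up to 30 Visit 4 attendances are then exposed to the release gap, provided the Visit 2 tests are repeated there. The number of misread pairs cannot be computed from the documents. The calculated range for false change, 0.75 to 7.5 of 30, is an upper one; independence between visits halves it to 0.375 to 3.75. Confidence is high on the wording and low on the size of any consequence. Severity: minor.

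**What to change.** Put the same rule in both sections:

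> For each studied exacerbation (Visit 2 or Visit 4), antibiotics are withheld until that visit's samples are taken and then started if prescribed; the hold lapses at once if the patient cannot attend or is hospitalised; all other exacerbations are treated as usual.

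The lapse clause makes explicit what Study design implies when it says hospitalised patients, and those unable to attend, are not studied. No release point is given for them at present.

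Optionally, use the treatment diary to flag any sample taken after an antibiotic dose, and repeat the bacterial classification and the stability analysis without those samples. The diary is listed under Visits 1, 2 and 3 only, so the plan would need to say that it also applies at Visit 4.

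The cost is one reworded sentence in each of two sections, with no new visits or assays.
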